### 7.5.1.3 Subgroup Analyses

In order to assess whether or not AEs vary across specific patient groups, AE occurrence will be summarized by SOC and PT for the subgroups specified in section [7.8](#).

## 7.5.2 Clinical Laboratory Evaluation

### All Laboratory Tests

For clinical laboratory parameters (hematology, chemistry, urinalysis and fast lipid profile), raw values at each scheduled visit, change from baseline at each post-baseline visit, shift from baseline and shift from reference range will be summarized using descriptive statistics or frequency tabulation. No statistical hypothesis testing will be performed. For Fasting Lipids Profile, all analysis will be conducted using the measured values which are confirmed under fasting condition. In addition, all Lipid Profile values including non-fasting condition will also be summarized for descriptive statistics.

- For continuous variables, descriptive statistics of Raw values at each scheduled visit will be summarized at each time point using SI unit. For the ratio T-Chol to HDL and the ratio LDL to HDL, descriptive statistics will be summarized at each post-baseline visit.
- For continuous variables, descriptive statistics of change from baseline value will be summarized at each post-baseline visit using SI unit.
- For categorical variables, frequencies and percentage will be displayed at each scheduled visit.
- Shift-from-baseline table: Shift from baseline to highest value up to Week 12 or during entire period, and baseline to lowest value up to Week 12 or during entire period, for all laboratory variables. If the laboratory value of same subject is measured lower from normal range at one visit, and higher from normal range at the other visit, that subject will be counted as both low and high from baseline up to Week 12 or during entire period.

### **Laboratory Tests for NCI-CTC Toxicity Grading**

Laboratory test results for the select laboratory tests will be graded programmatically using the standardized NCI-CTC toxicity grading criteria (Grade 0, 1, 2, 3, 4) specified in the 10.8 Appendix8 for this study. Shift-from-baseline to worst value up to Week 12 or during entire period will be provided.

Note: AEs in this study are graded the investigator using NCI-CTAE Grade (1, 2, 3, 4, 5).

### **Laboratory Tests for Reference Range**

Test results for the select laboratory tests in Table 3 will be summarized against the reference range indicated. Number and percentage for the Highest/Lowest values of each subjects included in pre-specified reference range for select laboratory up to Week 12 or during entire period, will be provided.

**Table 3. Select Laboratory Variables and Corresponding Reference Ranges**

Select Laboratory Variable	Reference Range	Highest/Lowest
Aspartate Aminotransferase (AST)	$\geq 1 \times \text{ULN}$ to $< 2 \times \text{ULN}$ $\geq 2 \times \text{ULN}$ to $< 3 \times \text{ULN}$ $\geq 3 \times \text{ULN}$	Highest
Alanine Aminotransferase (ALT)	$\geq 1 \times \text{ULN}$ to $< 2 \times \text{ULN}$ $\geq 2 \times \text{ULN}$ to $< 3 \times \text{ULN}$ $\geq 3 \times \text{ULN}$	Highest
Alkaline Phosphatase (ALP)	$> 2 \times \text{ULN}$ to $\leq 3 \times \text{ULN}$ $> 3 \times \text{ULN}$ to $\leq 5 \times \text{ULN}$ $> 5 \times \text{ULN}$	Highest
Total Bilirubin	$> 1.5 \times \text{ULN}$	Highest
Total Bilirubin	$\geq 1 \times \text{ULN}$ to $< 2 \times \text{ULN}$ $\geq 2 \times \text{ULN}$ to $< 3 \times \text{ULN}$ $\geq 3 \times \text{ULN}$	Highest
Low-Density Lipoprotein (LDL)	$> 160 \text{ mg/dL}$	Highest
Low-Density Lipoprotein (LDL)	$< 100 \text{ mg/dL}$ 100 to $< 130 \text{ mg/dL}$ 130 to $< 160 \text{ mg/dL}$ 160 to $< 190 \text{ mg/dL}$ $\geq 190 \text{ mg/dL}$	Highest
Hemoglobin (HGB)	$\geq 8.0$ to $< 10.0 \text{ g/dL}$ $< 8.0 \text{ g/dL}$	Lowest
Hemoglobin (HGB)	$\geq (\text{Baseline-2})$ to $< (\text{Baseline-1}) \text{ g/dL}$ $< (\text{Baseline-2}) \text{ g/dL}$	Lowest
Hemoglobin (HGB)	
 
Mild to Moderate: decrease from baseline <math>\geq 1</math> to <math>\leq 2 \text{ g/dL}</math>,
 
Severe: decrease from baseline <math>> 2</math> to <math>< 3 \text{ g/dL}</math> or absolute value <math>> 7</math> and <math>< 8 \text{ g/dL}</math>,
 
Potentially Life Threatening: decrease from baseline <math>\geq 3</math> or absolute value <math>\leq 7 \text{ g/dL}</math>
 
	Lowest
Creatine Phosphokinase (CPK)	$> 500$ to $\leq 2,000 \text{ U/L}$ $> 2,000 \text{ U/L}$	Highest
Creatine Phosphokinase (CPK)	$> 5 \times \text{Baseline}$	Highest
Creatine Phosphokinase (CPK)	$> 2 \times \text{ULN}$ to $\leq 5 \times \text{ULN}$ $> 5 \times \text{ULN}$ to $\leq 10 \times \text{ULN}$ $> 10 \times \text{ULN}$	Highest

Select Laboratory Variable	Reference Range	Highest/Lowest
Creatinine	> 1.5 × Baseline to ≤ 3.0 × Baseline > 3.0 × Baseline	Highest
Absolute Neutrophil Count (ANC)	≥ 1,500 to < 2,000 / mm  ≥ 500 to < 1,500 / mm  < 500 / mm 	Lowest
Lymphocytes	≥ 200 to < 500 /uL < 200 /uL	Lowest
Lymphocytes	≥ 1,500 to < 2,000 / mm  ≥ 500 to < 1,500 / mm  < 500 / mm 	Lowest
Platelets	≥ 2 × 10  to < 5 × 10  /uL < 2 × 10  /uL	Lowest
Platelets	> 600,000 /uL	Highest
ULN = Upper Limit Normal Each categories are mutually exclusive.		

### 7.5.2.1 Liver Abnormalities

The following potentially clinically significant criteria in liver function tests for Alkaline Phosphatase (ALP), Alanine Transaminase (ALT), total bilirubin, Aspartate Transaminase (AST) and their combination are defined. The subject's highest value during the investigational period will be used.

Parameter	Criteria
ALT	> 3xULN
	> 5xULN
	> 10xULN
	> 20xULN
AST	> 3xULN
	> 5xULN
	> 10xULN
	> 20xULN
ALT or AST	> 3xULN
	> 8xULN
Total Bilirubin	> 2xULN
ALP	> 1.5xULN

ALT and/or AST OR Total Bilirubin (\*) (ALT and/or AST > 3xULN) or  
total bilirubin > 2xULN

ALT and/or AST AND Total Bilirubin (\*) (ALT and/or AST > 3xULN) and total bilirubin  
> 2xULN

(\*) Combination of values measured within same sample

The number and percentage of subjects with potentially clinically significant values in liver function tests during the investigational period will be presented by treatment group.

Additionally, confirmed liver abnormalities will be characterized as moderate and marked, as follow:

Moderate: ALT or AST > 3×ULN OR Total Bilirubin > 2×ULN.

Marked: ALT or AST > 3×ULN AND Total Bilirubin > 2×ULN.

Number and percentage of subjects in each category at each scheduled visit will be summarized. These combinations of elevated values are based on measured value within the same sample.

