Study discontinuation	The act of concluding participation, prior to completion of all protocol-required elements, in a study by an enrolled subject. Four categories of discontinuation are distinguished: a) dropout: Active discontinuation by a subject (also a noun referring to such a discontinued subject); b) discontinuation initiated by the investigator or other responsible personnel (e.g., for cause); c) loss to follow-up: discontinuation of participation without notice or action by the subject; d) sponsor-initiated discontinuation. Note that subject discontinuation does not necessarily imply exclusion of subject data from analysis.
Enroll	To register or enter into a clinical study; transitively and intransitively. Informed consent precedes enrollment, which precedes or is contemporaneous with randomization.
Investigational period	The period of time where major interests of protocol objectives are observed. In general, the subject will receive a test drug or comparative drug (possibly without randomization) during this period, which extends until the last post-treatment assessment is completed.
Follow-up period	The follow-up period will be 4 weeks (on a per-protocol basis) starting after the early-termination visit for withdrawn subjects and after the Week 52 visit for subjects who completed the study but are not willing to enroll into the extension study. For subjects who completed the study and wish to enroll into the extension study, the follow-up period will last for a maximum of 4 weeks starting after the Week 52 visit and ending at the initiation of the extension study treatment.
Randomization	Action to allocate a subject to the treatment group or treatment cohort. Depending on the type of rules for handling for study drugs, 'Randomization' is usually executed just before entering the 'investigational period.'
Screening	1) Process of searching for candidates for the study 2) Process of checking the eligibility of subjects, usually done during the "pre-investigational period"
Screening failure	Screened subject, but did not fulfill protocol inclusion and/or exclusion criteria and failed to receive randomized or open label study treatment, or decided not to participate anymore (withdrew consent) prior to completing pre-investigational period.

- CONFIDENTIAL -

Terms	Definition of terms

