APPENDIX <4>: LIVER SAFETY MONITORING AND ASSESSMENT

If laboratory testing for a subject enrolled in the study and receiving the study drug reveals an increase in serum aminotransferase (ALT, AST) $> 3 \times \text{ULN}$ or TBL $> 2 \times \text{ULN}$, the investigator/sub-investigator should repeat at least 4 parameters (ALT, AST, ALP, and TBL) of the usual hepatic function test parameters. Retesting should be performed between 48 hours and 72 hours after notification of the test results. For studies for which a central laboratory () is used, alerts will be generated by the central laboratory regarding moderate and marked liver abnormality to inform the investigator or other responsible personnel and the sponsor. Subjects should be asked if they have any symptoms suggestive of hepatobiliary dysfunction by the investigator/sub-investigator.

Definition of Hepatic Function Abnormal

Confirmed hepatic function abnormal will be characterized as moderate (hepatocellular failure type or cholestasis type) or marked (mixed type) based on the ULN as follows:

	ALT or AST		TBL
Moderate			
Hepatocellular failure type	$> 3 \times \text{ULN}$	or	$> 2 \times \text{ULN}$
or			
cholestasis type			
Marked			
Mixed type	$> 3 \times \text{ULN}$	and	$> 2 \times \text{ULN}$

In addition, the subject with any of the following should be considered to have marked (severe) hepatic function abnormal.

ALT or AST $> 8 \times \text{ULN}$

ALT or AST $> 5 \times \text{ULN}$ for more than 2 weeks

ALT or AST $> 3 \times \text{ULN}$ and INR > 1.5

ALT or AST $> 3 \times \text{ULN}$ with the appearance of fatigue, nausea, vomiting, right upper quadrant pain or tenderness, pyrexia, rash and/or eosinophilia ($> 5\%$)

If the investigator/sub-investigator determines that abnormal liver function results, other than as described above, qualify as moderate or marked abnormalities, they should conduct additional monitoring and follow-up.

Follow-up Procedures

Confirmed moderate and marked hepatic function abnormal should be thoroughly characterized by obtaining appropriate expert consultations, detailed pertinent history, physical examination and laboratory tests by the investigator/sub-investigator. The investigator should complete the liver abnormality case report form (LA-CRF) or an appropriate document. Subjects with confirmed abnormal liver function test results should be followed as described below by the investigator/sub-investigator.

- CONFIDENTIAL -

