### **Liver Functions Plots**

A matrix scatter plot of liver function test will be plotted showing the maximum ALT, AST, ALP and total bilirubin during study period crossed against each other. Different dots will be used for randomization arm.

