**7.11.5 Handling of Schedule of Assessments of Safety Variables**

For data obtained after the end of study treatment, the data obtained within + 2 days after the last dose is taken will be included in analysis. Baseline for safety is defined as last non-missing value before the first dose of study drug for all subjects including placebo assigned subjects. For Week 12/ET, or Week 28/ET, the values at closest date to reference date will be used. As for the subjects who switched to receive ASP015K instead of placebo at Week 12, the last observation before first dose of ASP015K at Week 12 will be used for the analysis for visit Week 4, 8, 12, 12/ET. In addition, the subjects who switched to receive ASP015K instead of placebo at Week 28, the last observation before the first dose of ASP015K at Week 28 will be used for the analysis for visit Week 4, 8, 12, 12/ET, 28/ET. For EOT, the closest value to the reference date will be used regardless of the switching from placebo.

(1) Vital signs, laboratory test (hematology, biochemistry, urinalysis)

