**Table10. Visit Window for Vital signs, laboratory test (hematology, biochemistry, urinalysis)**

Time points defined in analysis	Reference date*	Acceptable time range
Screening	Day -28 to Day -1	Day -28 to Day -1
Baseline	Day 1	Day 1
Week 4 to Week 48**	Day $7 \times x + 1$	Day $(7 \times x - 6)$ to Day $(7 \times x + 8)$ and before drug administration on the visit day
Week 52	Day 365	Day 358 to Day 372
Minimum on Treatment up to Week 12***		Minimum value at allowance Range (Day 2 to Day 92) before first dose of Week 12 study drug
Maximum on Treatment up to Week 12***		Maximum value at allowance Range (Day 2 to Day 92) before first dose of Week 12 study drug
Minimum on Treatment***		Minimum value during Entire Period (No limitation for period)
Maximum on Treatment***		Maximum value during Entire Period (No limitation for period)
Week 12/ET (Week 12 or at early termination before Week 12)	Day 85	Day 2 to Day 92
Week 28/ET (Week 28 or at early termination before Week 28)	Day 197	Day 2 to Day 204
EOT (Week 52 or at early termination)	Day 365	Day 2 to Day 372

\*: Day 1 represents the first day of study treatment. The day before is expressed as Day -1.

\*\* : Represents the reference date and acceptable time range for Week x.

\*\*\*: Applied to laboratory test only.

(2) Laboratory test (fasting lipid profile test)

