Shift-from-Baseline Table for Laboratory Test Results, Fasting Lipid Profile Baseline to Lowest Value up to Week 12	X1	X3
Shift-from-Baseline Table for Laboratory Test Results, Fasting Lipid Profile Baseline to Week 12/ET	X1	X3
Shift-from-Baseline Table in Pre-Specified Reference Range Laboratory test Results by Visit, Selected Laboratory Variables		
Aspartate Aminotransferase (AST)	X1	X2
Alanine Aminotransferase (ALT)	X1	X2
Alkaline Phosphatase (ALP)	X1	X2
Total Bilirubin Category 1	X1	X2
Total Bilirubin Category 2	X1	X2
Low-Density Lipoprotein (LDL)	X1	X2
Hemoglobin (HGB) Category 1	X1	X2

Hemoglobin (HGB) Category 2	X1	X2
Hemoglobin (HGB) Category 3	X1	X2
Creatine Phosphokinase (CPK) Category 1	X1	X2
Creatine Phosphokinase (CPK) Category 2	X1	X2
Creatine Phosphokinase (CPK) Category 3	X1	X2
Creatinine	X1	X2
Absolute Neutrophil Count (ANC)	X1	X2
Lymphocytes Category 1	X1	X2
Lymphocytes Category 2	X1	X2
Platelets Category 1	X1	X2
Platelets Category 2	X1	X2
Shift-from-Baseline Table for Selected Laboratory Variables using NCI-CTCAE Toxicity Grade (version 4.0) Baseline to Week 12/ET	X1	X3
Liver Function Analysis Clinically Significant Values in Liver Function Tests	X1	X2
Summary of Moderate and Marked Liver Abnormalities by Visit	X1	X2
Liver Functions Plots	X1	X2
Vital Signs		
Vital Signs Actual and Change from Baseline	X1	X2
ECG Results by Local Investigator		
Interpretation of 12- Lead ECG Results, Assessment by Investigator Shift-from-Screening Table for 12-Lead ECG	X1	X2
Central ECG Results		
Summary of Central ECG Results Actual and Change From Baseline	X1	
Summary of Central ECG Results Change From Predose to Postdose at Week 4/ Week 8	X1	
Number and Percentage of Subjects with Categorized Central ECG Parameter Low Extreme Values	X1	
Number and Percentage of Subjects with Categorized Central ECG Parameter High Extreme Values	X1	
Number and Percentage of Subjects with Categorized Central ECG Parameter Low Extreme Values Change From Baseline	X1	
Number and Percentage of Subjects with Categorized Central ECG Parameter High Extreme Change Values Change From Baseline	X1	
Number and Percentage of Subjects with Categorized	X1	

Central ECG Parameter Low Extreme Change Values Change From Predose to Postdose at Week 4/ Week 8 Number and Percentage of Subjects with Categorized Central ECG Parameter High Extreme Change Values Change From Predose to Postdose at Week 4/ Week 8	X1	
---	----	--

X1: Placebo, 100mg, 150mg

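### SAP 7.5.2.1 borrows the protocol's *marked* liver label but applies only one of the five routes that Protocol Appendix 4 places under it

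*SAP*

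**What the plan says.** SAP 7.5.2.1 has two sets of liver counts.

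The first is a list of potentially clinically significant criteria for ALT, AST, ALP, bilirubin and their combinations. Here the subject's "highest value during the investigational period will be used", except that the combination rows require values from one sample. The list includes ALT or AST above 8×ULN, and ALT and AST each above 5×ULN with no duration attached.

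The second classifies confirmed abnormalities. *Moderate* is ALT or AST above 3×ULN or bilirubin above 2×ULN. *Marked* is ALT or AST above 3×ULN and bilirubin above 2×ULN. These are counted by scheduled visit: "These combinations of elevated values are based on measured value within the same sample". SAP Appendix 4, Table 18 lists the output as "Summary of Moderate and Marked Liver Abnormalities by Visit". A separate figure is planned, "showing the maximum ALT, AST, ALP and total bilirubin during study period crossed against each other".

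Protocol Appendix 4 defines the same two labels by the same thresholds. It then adds that "the subject with any of the following should be considered to have marked (severe) hepatic function abnormal" and gives four further criteria.

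On timing, SAP 7.11.5 opens with a general rule for samples taken after treatment ends: "the data obtained within + 2 days after the last dose is taken will be included in analysis". Table 10, inside that section, sets the laboratory maximum on treatment as "Maximum value during Entire Period (No limitation for period"). The SAP key terms do not define the investigational period used in 7.5.2.1. The protocol's definition describes it as a period "which extends until the last post-treatment assessment is completed".

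**The concern.** In the protocol, *marked* carries consequences. Without another cause it may be reported as a serious adverse event, and the sponsor is to be told of every case possibly due to study drug. The Appendix 4 criteria for considering discontinuation of treatment are the same five routes. Someone reading a study-report table headed *moderate* and *marked* will take the second column as the number of subjects who reached that level. Under the SAP it is the number who reached it by one route only. Isolated high or prolonged ALT, which the protocol treats as *marked*, would be shown as *moderate*. Liver events of this grade are expected to be few, so one or two reclassified subjects can decide whether an arm shows none or some.

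**Working it through.** No figure in the plan can be reproduced here; the check is a comparison of definitions.

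**Routes to *marked*.**

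| Route in Protocol Appendix 4 | SAP *marked*? | Where SAP 7.5.2.1 shows it if bilirubin is not above 2×ULN |
|---|---|---|
| ALT/AST >3×ULN and bilirubin >2×ULN | Yes | Not applicable |
| ALT/AST >8×ULN | No | *Moderate*; own whole-period row |
| ALT/AST >5×ULN for more than 2 weeks | No | *Moderate*; >5×ULN rows, no duration |
| ALT/AST >3×ULN and INR >1.5 | No | *Moderate*; >3×ULN rows |
| ALT/AST >3×ULN with symptoms, rash or eosinophilia | No | *Moderate*; >3×ULN rows |

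The SAP keeps 1 of 5 routes.

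**Hypothetical subjects run through both rules.**

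- ALT 4×ULN and bilirubin 2.5×ULN in one sample: *marked* in both.
- ALT 9×ULN, bilirubin 1×ULN: *marked* in Appendix 4, *moderate* in the SAP.
- ALT 6×ULN in two samples 21 days apart, bilirubin 1×ULN: *marked* and *moderate* respectively.
- ALT 4×ULN with INR 1.7, or ALT 4×ULN with symptoms, bilirubin 1×ULN: *marked* and *moderate* respectively.
- ALT 4×ULN, then 3 days later ALT 2.8×ULN with bilirubin 2.5×ULN: *moderate* in the SAP. Both thresholds are met on the subject's peak values, as the planned figure would show. Appendix 4 does not say whether different samples may be combined.

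**Which routes can be tabulated.** ALT and AST are in the scheduled central-laboratory panel (Protocol 5.4.4), so the second and third routes need no new data. INR is not in that panel and appears in Appendix 4 only as a possible extra test. The symptom route rests mainly on clinical data. A by-visit table cannot show a duration, so the third route needs a subject-level row.

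**Size of one subject.** With the planned 170 per arm, one subject is 1/170 = 0.59 percentage points. Exact 95% intervals: 0/170 is 0% (0 to 2.1%), 1/170 is 0.6% (0.01 to 3.2%), 2/170 is 1.2% (0.1 to 4.2%). The range of 0 to 2 reclassified subjects per arm is an assumption for illustration.

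**Why the post-dose window should be stated.** Follow-up biochemistry is due 28 ± 7 days after early termination, that is 21 to 35 days. If early termination falls on the day of the last dose (assumed), this is 21 − 2 = 19 to 35 − 2 = 33 days past the limit in 7.11.5, but inside both the Table 10 maximum and the investigational period. The duration route is affected too. More than 2 weeks needs a second sample at least 15 days after the first. If drug stops *k* days after the first, the limit is day *k* + 2, so the earliest confirming sample is 15 − (*k* + 2) = 13 − *k* days too late: 13 days at *k* = 0, 1 day at *k* = 12, none at *k* = 13.

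**The case against.** The best defence is that little is lost. The SAP reproduces Appendix 4's definition table, and the four other criteria follow it as additions. ALT/AST above 8×ULN is counted in its own row. Values above 5×ULN are counted for each enzyme, and again as Grade 3 or higher in the planned shift to worst toxicity grade. The INR and symptom routes cannot be fully derived from scheduled laboratory data. No hypothesis test is run on laboratory data (SAP 7.5.2). Combined elevations must be reported to the sponsor as for serious events whatever the investigator decides (Protocol 5.4.4.2), and Hy's Law cases are always serious (Protocol Appendix 3). All of this stands and keeps the point minor. It does not remove the mismatch: the additions are *marked* by the protocol's own wording, and the SAP uses that word without them.

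Two stronger readings are tempting. A reader might infer that the same-sample rule contradicts the protocol. It does not. Appendix 4 and 5.4.4.2 are silent on it, the four liver tests are to be repeated together, and judging a combination on one sample is a legitimate convention. Subjects with staggered peaks still appear in the single-parameter rows, the either-or row and the maximum-value figure.

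A reader might also infer that the SAP sets irreconcilable post-dose cut-offs. Two of the three statements agree: the Table 10 maximum and the investigational period both reach follow-up. The Table 10 row, which its footnote confines to laboratory tests, reads naturally as a specific exception to the general 2-day sentence. What remains is some ambiguity, because the row is labelled as on treatment and no exemption is stated. Subjects who enter the extension directly after Week 52 have no follow-up visit, which narrows it further.

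**Conclusion.** The labelling mismatch is real and minor. SAP *marked* is a strict subset of protocol *marked*, so its count can be understated but never overstated on this account. The conclusion rests only on the two definitions. The documents give no rates for the four omitted routes or for a late bilirubin rise, so the number of subjects affected cannot be estimated; the 0.59-point step shows what one subject is worth in an arm of 170, not an expected bias. Table 18 also reports liver results for six treatment-sequence groups, which split the placebo arm four ways, so one subject weighs more there. It would be wrong to infer that serious liver cases go unreported or that any efficacy conclusion is touched. The same-sample convention and the timing wording are not errors; each merits only a small addition.

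**What to change.** - Add a subject-level, whole-period *marked* row that includes ALT/AST above 8×ULN and above 5×ULN for more than 2 weeks, derived from all scheduled and unscheduled central-laboratory results, and say how the duration is judged. List INR and symptom cases from the liver case report form. Alternatively, rename the SAP category so that it is not read as the protocol's.
- Keep the same-sample row. As a cheap addition, count subjects whose peak ALT/AST is above 3×ULN and peak bilirubin above 2×ULN at any time, to match the planned figure, with a listing of sample dates.
- Add one sentence: whole-period liver rows follow the unlimited period in Table 10 and are exempt from the 2-day rule in 7.11.5.

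The cost is two or three sentences, one or two table rows and one listing, from data already collected. The SAP leaves table and listing formats to a separate specification, so a suitable listing may already exist. The one drawback is that the any-time count may pick up an unrelated later bilirubin rise, which the dated listing would expose.
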